There will be no randomization. Study participants will be treated with deoxycholic acid (Kybella) 10 mg/ mL injected subcutaneously, targeting the medial thigh deep fat compartment (pre-fascial). Subjects will receive deoxycholic acid 2 mg/ cm², with injections of 0.2 mL spaced evenly 1 cm apart within the treatment area. Bilateral upper inner thighs will be treated. Each treatment will consist of a maximum of 8 mL (40 injection sites) of the study drug, with a maximum of 4 mL (20 injection sites) of the study drug for each thigh. All treatments will be performed by a study physician. Subjects will receive 1 to 4 treatment sessions, each spaced 6 weeks +/- 1 week. Treatment #2, #3, or #4 will be pursued if patient desires more treatment, and if there is sufficient fat for treatment, per investigator's judgment.

V. Study Procedures

a) Study visits and parameters to be measured
 All visits in this study will be performed at the UCSD Dermatology Clinic, 3rd floor,
 [name].

Screening/Baseline Visit (Visit 1, Day -14 to 1)

This visit is expected to take approximately 1 hour. The following describes the procedures performed at this visit.

Prior to any screening assessments, informed consent will be obtained by the
investigator. When the subject fully understands the nature of the study and its risks,
the subject will be asked to sign and date the informed consent form. The
investigator will then sign and date the form.

- 2. A detailed medical history of information pertaining to treatment will be obtained.
- 3. The investigator will perform a relevant physical examination.
- 4. Patient's weight will be obtained.
- 5. The subject will be asked to complete the Subject Self-Rating Scale (0 to 6 scale).
- 6. If the subject meets the criteria for the study, the subject will be assigned the next consecutive subject number.
- 7. Females of childbearing age will undergo a urine pregnancy test
- 8. The investigator will determine the patient's eligibility for the study.

First treatment (Visit 2, Day 1)

The treatment visit is expected to take approximately 1 hour. The first treatment may be combined with Screening/ Baseline.

Prior to Kybella treatment:

- 1. Patient will be asked to complete the Subject Self-Rating Scale, rated from 0 to 6.
- 2. Patient's weight will be obtained.
- 3. Concomitant medications and procedures will be confirmed and recorded.
- 4. The investigator will perform a relevant physical examination.

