- 5. Thigh circumference measurement will be obtained with anthropometric tape measure.
 - Thigh circumference will be measured at site of maximum bulge at Screening.
 Vertical distance of this site from the floor will be measured, such that thigh circumference measurements at all following study assessments are performed at the same site.
- 6. Caliper measurement of inner thigh skin-fold thickness will be obtained.

Caliper measurement will be performed at site of maximum bulge at Screening.
 Vertical distance of this site from the floor will be measured, such that caliper measurements at all following study assessments are performed at the same site.

- 7. Thigh gap measurement will be obtained.
 - Patient will be asked to stand with legs at a fixed distance apart. Measurement
 will be performed between sites of maximum bulge at Screening. Vertical
 distance of these sites from the floor will be measured, such that thigh gap
 measurements at all following study assessments are performed at the same sites.
- 8. Pre-treatment photographs will be taken.
 - Patients will be asked to stand with feet apart at a uniform distance.

 Anteroposterior and posteroanterior photos will be taken.

Treatment:

9. Deoxycholic acid (Kybella) 10 mg/ mL will be injected subcutaneously, targeting the medial thigh deep fat compartment (pre-fascial). Subjects will receive deoxycholic acid 2 mg/ cm2, with injections of 0.2 mL spaced evenly 1 cm apart within the treatment area. Bilateral thighs will be treated. Each treatment will consist of a maximum of 8 mL (40 injection sites) of the study drug, with a maximum of 4 mL (20 injection sites) of the study drug for each thigh. All treatments will be performed by a study physician.

Post-Treatment Phone Call #1 (Day 3)

Phone call expected to take 5-10 minutes.

1. Two days after treatment, patient will be called and asked to report adverse events since last treatment. All adverse events will be recorded.

Second treatment (+/-) (Day 36 to 50)

The treatment visit is expected to take approximately 1 hour.

Prior to Kybella treatment:

1. Patient will be asked to complete the Subject Self-Rating Scale, rated from 0 to 6.

- 2. Patient's weight will be obtained.
- 3. Concomitant medications and procedures will be confirmed and recorded.
- 4. Adverse events will be recorded.
- 5. The investigator will perform a relevant physical examination.
- 6. Thigh circumference measurement will be obtained with anthropometric tape measure.

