 distance of these sites from the floor will be measured, such that thigh gap
 measurements at all following study assessments are performed at the same sites.
- 10. Follow-up photographs will be taken.
 - Patients will be asked to stand with feet apart at a uniform distance.
 Anteroposterior and posteroanterior photos will be taken.

b) Drugs to be used

Deoxycholic acid (Kybella) 10 mg/ mL will be injected subcutaneously, targeting the medial thigh deep fat compartment (pre-fascial).

c) Data to be collected and when data is to be collected

Data to be collected throughout the study includes the items listed in Schedule of Events.

VI. Biostatistical Analysis

A. Study endpoints

1. Primary Endpoint:

The primary endpoint will be safety endpoint, as defined by the incidence rate of patients who experience:

- a) Any adverse event (AE) ascertained by patient report or physician evaluation
- b) One or more serious adverse events (SAE) as defined by CTCAEv4
- c) Adverse events leading to study drug discontinuation.

2. Secondary Endpoints:

- a) Efficacy, defined as reduction in inner thigh fat, measured as follows:
 - i. Change in thigh circumference, as recorded with anthropometric tape measure.
 - Thigh circumference will be measured at site of maximum bulge at Screening. Vertical distance of this site from the floor will be measured, such that thigh circumference measurements at all following study assessments are performed at the same site.
 - ii. Change in inner thigh skin-fold thickness, as measured by calipers
 - Caliper measurement will be performed at site of maximum bulge at Screening. Vertical distance of this site from the floor will be measured, such that caliper measurements at all following study assessments are performed at the same site.
 - iii. Increase in "thigh gap," measured with patient standing with legs at a fixed distance apart. Measurement will be performed between sites of maximum bulge at Screening. Vertical distance of these sites from the floor will be measured, such that thigh gap

measurements at all following study assessments are performed at the same sites.

- iv. Percent accuracy by three blinded physicians in correctly identifying baseline photographs, upon independent review of before-and-after clinical photographs of the treatment area.
- Patients will be asked to stand with feet apart at a uniform distance.

 Anteroposterior and posteroanterior photos will be taken.

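### Caliper readings are to be repeated at the same site, but only its height above the floor is recorded, so the front-to-back position of the skin-fold is not fixed

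*Combined protocol and SAP*

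**What the plan says.** All references are to the combined protocol and SAP.

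- **Endpoint.** Section VI.A.2.a.ii lists, among the secondary efficacy measures, "Change in inner thigh skin-fold thickness, as measured by calipers". Section VI.B reports it descriptively, in the ITT population.
- **Where the fold is taken.** Section V.a, First treatment, item 6: "Caliper measurement of inner thigh skin-fold thickness will be obtained". The position is then defined: "Caliper measurement will be performed at site of maximum bulge at Screening".
- **How it is found again.** "Vertical distance of this site from the floor will be measured, such that caliper measurements at all following study assessments are performed at the same" […]. The instruction recurs at treatments 2 to 4, at the Week 4 and Week 12 follow-ups, and in the endpoint definition. It parallels the instruction for thigh circumference.
- **What is injected.** Section IV.D: "injections of 0.2 mL spaced evenly 1 cm apart within the treatment area", at 10 mg/mL and 2 mg/cm², with "a maximum of 4 mL (20 injection sites) of the study drug for each thigh" at each treatment. There are 1 to 4 treatments.
- **What is not given.** No horizontal coordinate, anatomical landmark, skin mark, template or tracing is described for the caliper point. A stance is specified for the thigh gap and for the photographs, but not for the caliper. Nothing states that the injection grid contains the caliper point.

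**The concern.** The plan presents the recorded height as the means by which later readings return to one site. For a circumference that works, because the tape goes round the whole limb at that level. A caliper fold is taken at one place on that level, so a second coordinate is needed and none is recorded.

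The screening bulge is a guide to position at baseline. It is a weaker guide later, because a successful treatment reduces the very feature used to find the place. The photographs are front and back views and are not described as an aid to relocation.

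A displaced fold mixes a change of site with a change in fat. Displacement towards untreated tissue dilutes a real reduction. The study is open-label and blinding is described only for the photograph reviewers, so an assessor's choice of fold could also lean towards an apparent reduction. There is no control arm in which site error would show, and with no recorded position a displaced reading could not be recognised afterwards.

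**Working it through.** **1. Reproduce the plan's volumes.** Inputs from Section IV.D: 0.2 mL per site; 20 sites per thigh and 40 in total at each treatment.
- 20 × 0.2 mL = 4 mL per thigh; 40 × 0.2 mL = 8 mL in total. Both agree with the plan.

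**2. Largest area injected per thigh in one session.** The plan states no area, so it is derived in two ways.
- By dose: 4 mL × 10 mg/mL = 40 mg; 40 mg ÷ 2 mg/cm² = 20 cm².
- By grid: 20 sites × about 1 cm² per site = 20 cm².

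**3. Distance from the centre to the edge.** The shape is not specified, so it is assumed.

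| Treated area per thigh | Assumed shape | Centre to edge, horizontally |
|---|---|---|
| 20 cm² (one session, or same grid re-injected) | square | √20 ÷ 2 = 2.24 cm |
| 20 cm² | 4 × 5 cm rectangle | 2.0 or 2.5 cm |
| 20 cm² | circle | √(20 ÷ π) = 2.52 cm |
| 10 cm² (10 sites) | square | √10 ÷ 2 = 1.58 cm |
| 80 cm² (4 sessions × 20 cm², no overlap) | square | √80 ÷ 2 = 4.47 cm |

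The cap applies to each treatment, and the plan does not say whether later sessions re-inject the same grid or cover new skin. After one full session, or with an identical grid each time, the margin is therefore roughly 2 cm. It widens as sessions cover new skin, up to about 4.5 cm.

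**4. Sensitivity to relocation error (illustration only).** The documents give no relocation error. Assume that the caliper point is at the centre of a square patch, and that horizontal error is normal with mean 0 and standard deviation s. The share of readings centred outside the patch is 2 × (1 − Φ(half-width ÷ s)).

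| Assumed s | 20 cm² patch (half-width 2.24 cm) |
|---|---|
| 0.5 cm | below 0.1% |
| 1 cm | 2.5% |
| 1.5 cm | 14% |
| 2 cm | 26% |
| 3 cm | 46% |

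For 80 cm² the half-width doubles, so each share applies at twice the s: 2.5% at 2 cm and 14% at 3 cm. The range is wide because it is driven by s, which is unknown. The table shows that the answer depends on how well the site is relocated. It does not estimate how often readings miss.

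**The case against.** The strongest reply is that the protocol gives more than a height. The fold must be on the inner thigh, at the screening bulge, and repeated at the same site. Eligibility (Section III.A) requires a discrete area of excess fat, and injections target the medial thigh, so the natural reading is that the caliper point lies in the treated bulge. A fold also has width, so one centred on the edge of the patch still lies partly over treated tissue. Finally, this is one of several secondary measures, reported descriptively with no test or decision rule.

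Most of this stands, and it limits the point. Four stronger readings are tempting, and the documents do not support them:

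- **That the assessor may pinch anywhere at the recorded level and still comply.** The wording confines the fold to the screening site, and a knowingly displaced fold would not comply. The gap is that an inadvertent displacement can be neither prevented nor detected from the recorded data.
- **That no more than 20 cm² per thigh is ever treated.** That is a cap for each session; the cumulative area could be as large as 80 cm².
- **That follow-up readings will in fact miss the treated tissue, or miss it at a given rate.** No figure in the documents supports a rate.
- **That the caliper is the only local measure of fat.** The thigh gap is also taken between the bulge sites, and photographs of the treatment area are reviewed.

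What the reply does not remove is that a verbal description is being relied on to reproduce a position that is never recorded in the horizontal direction.

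**Conclusion.** The point holds in a limited form. The relocation rule fixes the level of the caliper reading but not its front-to-back position, so it does not by itself deliver the repeatability it claims. The margin is roughly 2 cm from the centre of a square patch after one full session or with the same grid re-injected, smaller with fewer sites, and up to about 4.5 cm if four sessions covered separate skin. These distances rest on the stated dose and spacing, on an assumed patch shape and on a centred caliper point.

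The likely effect is added noise, with possible dilution or unblinded-assessor bias, in one descriptive secondary efficacy endpoint in 15 subjects without a control arm. Neither the direction nor the size of any bias in millimetres can be derived. The primary safety endpoint is not affected. Severity is minor: a cheap improvement, worth making because site error cannot be corrected once the readings have been taken.

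**What to change.** 1. When the baseline caliper reading is taken, record for each thigh a second coordinate: the distance along the tape, at the recorded height, from a fixed anatomical landmark to the caliper point. The tape is already in use for the circumference.
2. Record the fold direction and a fixed stance with it, and use height, tape distance, direction and stance at every later visit. Amend the repeated caliper instruction in Section V.a and the definition in Section VI.A.2.a.ii accordingly.
3. At each treatment session, record whether the caliper point lies within the injected grid. Treat this as descriptive information only. Keep caliper change reported for the full ITT population of Section VI.B, because restricting it to points inside the grid would select subjects on a feature determined after baseline.

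The cost is one extra tape reading per thigh at baseline, one yes/no field per thigh at each session, a wording change, and about a minute per visit. No dose, schedule or treatment rule changes.

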nodules were sometimes noted, resolving within 30 days at most. Otherwise, no atrophy or other side effects were noted.¹⁵

One pilot study of PC/DC for injection lipolysis of the hips and upper lateral thigh showed favorable safety and efficacy results. Fifteen women were treated. Fat reduction was confirmed with circumferential measurements and ultrasound. Treatment with PC/DC was well-tolerated, with side effects limited to local injection-site reactions, including pain, erythema, and edema; itching and bruising occurred in one subject. Reduction in cholesterol, triglycerides, and low-density lipoprotein was noted; this was attributed to phosphatidylcholine. There were no significant adverse lab abnormalities associated with the procedure, including in renal and liver function. The procedure was well tolerated and 73% of patients reported satisfaction. ¹⁶

There are no previous reports of deoxycholic acid injection alone as a treatment for upper inner thigh fat.

C. Rationale behind the proposed research, and potential benefits to patients and/or society

The use of deoxycholic acid injection for treatment of upper inner thigh fat has not been previously studied. Deoxycholic acid injection has been studied extensively for submental fat. The proposed doses of deoxycholic acid in the present clinical trial have been shown to be systemically safe based on previous large clinical trials. The concept of an injectable treatment for body contouring has been present for years, but high-quality studies are lacking. A pilot study of phosphatidylcholine together with deoxycholic acid in the region of the hips and thighs has yielded safe and favorable results. Due to the safety and effectiveness of deoxycholic acid for submental fat, we hypothesize that deoxycholic acid is a safe and effective treatment for upper inner thigh fat. The results of the present clinical trial may lead to development of a new treatment option for upper inner thigh fat.

II. Specific Aims

A. Specific objectives and hypotheses to be tested in the research project

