 Vertical distance of this site from the floor will be measured, such that thigh circumference measurements at all following study assessments are performed at the same site.

- 7. Caliper measurement of inner thigh skin-fold thickness will be obtained.
- Caliper measurement will be performed at site of maximum bulge at Screening.
 Vertical distance of this site from the floor will be measured, such that caliper measurements at all following study assessments are performed at the same site.
- 8. Thigh gap measurement will be obtained.
- Patient will be asked to stand with legs at a fixed distance apart. Measurement
 will be performed between sites of maximum bulge at Screening. Vertical
 distance of these sites from the floor will be measured, such that thigh gap
 measurements at all following study assessments are performed at the same sites.
- 9. Pre-treatment photographs will be taken.
- Patients will be asked to stand with feet apart at a uniform distance.
 Anteroposterior and posteroanterior photos will be taken.

Treatment:

10. Deoxycholic acid (Kybella) 10 mg/ mL will be injected subcutaneously, targeting the medial thigh deep fat compartment (pre-fascial). Subjects will receive deoxycholic acid 2 mg/ cm2, with injections of 0.2 mL spaced evenly 1 cm apart within the treatment area. Bilateral thighs will be treated. Each treatment will consist of a maximum of 8 mL (40 injection sites) of the study drug, with a maximum of 4 mL (20 injection sites) of the study drug for each thigh. All treatments will be performed by a study physician.

Post-Treatment Phone Call #4 (~Day 108 to 150)

Phone call expected to take 5-10 minutes.

1. Two days after treatment, patient will be called and asked to report adverse events since last treatment. All adverse events will be recorded.

Week 4 Follow Up (~Day 134 to 176)

Visit expected to take 1 hour. The visit will take place 4 weeks after the last treatment.

- 1. Patient will be asked to complete Subject Self-Rating Scale, rated from 0 to 6.
- 2. Patient will be asked to complete Post-Treatment Satisfaction Questionnaire.
- 3. Concomitant meds and procedures will be confirmed and recorded.
- 4. Adverse events will be confirmed and recorded.
- 5. Patient weight will be obtained.
- 6. A relevant physical exam will be performed by the investigator.
- 7. Thigh circumference measurement will be obtained with anthropometric tape measure.
 - Thigh circumference will be measured at site of maximum bulge at Screening.

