 Vertical distance of this site from the floor will be measured, such that thigh circumference measurements at all following study assessments are performed at the same site.
- 8. Caliper measurement of inner thigh skin-fold thickness will be obtained.
 - Caliper measurement will be performed at site of maximum bulge at Screening.
 Vertical distance of this site from the floor will be measured, such that caliper measurements at all following study assessments are performed at the same site.
- 9. Thigh gap measurement will be obtained.
 - Patient will be asked to stand with legs at a fixed distance apart. Measurement
 will be performed between sites of maximum bulge at Screening. Vertical
 distance of these sites from the floor will be measured, such that thigh gap
 measurements at all following study assessments are performed at the same sites.
- 10. Follow-up photographs will be taken.
 - Patients will be asked to stand with feet apart at a uniform distance.
 Anteroposterior and posteroanterior photos will be taken.

Week 12 Follow Up (~Day 190 to 232)

Visit expected to take 1 hour. The visit will take place 12 weeks after the last treatment.

- 1. Patient will be asked to complete Subject Self-Rating Scale, rated from 0 to 6.
- 2. Patient will be asked to complete Post-Treatment Satisfaction Questionnaire.
- 3. Concomitant meds and procedures will be confirmed and recorded.
- 4. Adverse events will be confirmed and recorded.
- 5. Patient weight will be obtained.
- 6. A relevant physical exam will be performed by the investigator.
- 7. Thigh circumference measurement will be obtained with anthropometric tape measure.
 - Thigh circumference will be measured at site of maximum bulge at Screening.
 Vertical distance of this site from the floor will be measured, such that thigh circumference measurements at all following study assessments are performed at the same site.
- 8. Caliper measurement of inner thigh skin-fold thickness will be obtained.
 - Caliper measurement will be performed at site of maximum bulge at Screening.
 Vertical distance of this site from the floor will be measured, such that caliper measurements at all following study assessments are performed at the same site.
- 9. Thigh gap measurement will be obtained.
 - Patient will be asked to stand with legs at a fixed distance apart. Measurement
 will be performed between sites of maximum bulge at Screening. Vertical

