Common side effects of deoxycholic acid injection are injection site reactions, including swelling, pain, numbness, redness, and hardness of treatment area. Bruising, itching, warmth, hardness, tingling or burning sensation, skin tightness, hair loss, open sores (ulcers), damage, and tissue cell-death (necrosis) around the injection site are other possible side effects.

Deoxycholic acid injection in submental fat has been rarely associated with nerve injury, headache, mouth or throat pain, hypertension, nausea, or difficulty swallowing.

Patients will be asked regarding allergy to medications. Allergic reaction may occur with any medication.

Subjects will be provided post-treatment instructions (see attached).

B. Psychosocial (non-medical) risks

We do not anticipate any psychosocial risks due to this study. However, if any participants experience emotional distress during the study we will assist them to resolve this stress with appropriate referrals. Steps to prevent this outcome will include detailed explanation of the study and what to expect from the study treatment.

VIII. Potential Benefits

A. Potential benefits to participating individuals

Subjects participating in the study may receive the benefit of reduced inner thigh fat due to the study treatment.

B. Potential benefits to society

The results of this study will help us acquire information that may lead to the development of a new treatment for reduction of inner thigh fat.

IX. Cost and Remuneration

a. Remuneration

Subjects will receive financial compensation for their participation in the study.

Screening and treatment visits will not be compensated. Subjects will receive \$50 per inperson follow-up visit. Therefore, subjects will receive a total of \$100 for completing the entire study.

b. Cost

There will be no cost to the patient to participate in this study.

X. Monitoring and Quality Assurance

A. Independent monitoring of source data

At this time, we do not anticipate a need for an independent monitor as our monitoring of the data will be sufficient to ensure the validity and integrity of the data and adherence to the IRB-approved protocol.

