Safety data will be collected at each visit of the study by study investigators and will be monitored by the Principal Investigator ([name]). Investigators will perform overall efficacy assessments of this study. The Principal Investigator will be reviewing data on an ongoing and consistent basis throughout the duration of the study. [name] will ensure that the study is conducted according to the protocol and that the data was accurately recorded. The Principal Investigator ([name]) is responsible for protecting the rights, safety, and welfare of subjects under his/her care. The Principal Investigator will be responsible for this review and for determining whether the research should be

altered or stopped. If any severe adverse effect or death directly related to the procedure proposed occurs, Principal Investigator will report to the IRB.

XI. Outcomes monitoring

Any adverse events will be reviewed and analyzed by the Principal Investigator as soon as the event occurs and will be documented in the subject's binder. Any unexpected adverse reactions will be reported by telephone to the IRB within 48 hours of observing the event. If a unexpected side effect occurs, Principal Investigator will also report adverse events to the FDA.

XII. Adverse event reporting guidelines

The principal investigator will follow the UCSD Human Research Committee guidelines for Adverse Event Reporting.

XIII. References

- Ingargiola M J, Motakef S, Chung M T, Vasconez H C, & Sasaki G H.
 Cryolipolysis for fat reduction and body contouring: safety and efficacy of current treatment paradigms. Plastic & Reconstructive Surgery. 2015;135(6):1581-1590.
- 3. Wollina U, & Goldman A. ATX-101 for reduction of submental fat. Expert opinion on pharmacotherapy. 2015;16(5):755-762.

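### After the 2-day call no adverse-event contact is scheduled for 26 to 56 days and no diary is described, so delayed reactions will be poorly characterised, although the any-AE rate would move little

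*Combined protocol and SAP*

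**What the plan says.** Section IV.D sets the spacing: "Subjects will receive 1 to 4 treatment sessions, each spaced 6 weeks +/- 1 week". Section V.a then gives the same telephone contact after every session: "Two days after treatment, patient will be called and asked to report adverse events since last treatment". The call is an open question; no list of reactions, dates or severity grades is attached to it.

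The next scheduled contact is the following treatment visit (Day 36 to 50 for session 2), where AEs are recorded and an examination is done before the injection. After the final session there are two follow-up visits: "The visit will take place 4 weeks after the last treatment" and "The visit will take place 12 weeks after the last treatment". Both list AE recording and a physical examination.

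Each treatment visit in V.a ends with the injection step. At sessions 2 to 4 the AE item comes before it; the list for the first session has no AE item. Section X.B states: "Safety data will be collected at each visit of the study by study investigators".

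Section VII.A lists the expected injection-site reactions and adds that "hair loss, open sores (ulcers), damage, and tissue cell-death (necrosis) around the injection site are other possible side effects". Section VI.A makes the primary endpoint the proportion of patients with any AE, with an SAE, or with an AE leading to discontinuation. Section VI.B adds that AEs will be explored for trends.

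**The concern.** The schedule looks closely once, at 2 days, and then not for several weeks. A reaction that begins after the call and clears before the next visit is not examined while it is present. With no diary, its type, start, end and worst severity come from what the subject remembers and volunteers, or from an unsolicited report.

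This matters because section I describes the study as the first use of deoxycholic acid alone at this site, safety is the primary objective, and there are 15 subjects. The submental experience cited in I.B is itself described partly by severity and duration, so readers will want the same description here. The trend review in VI.B needs event-level data that the schedule does not reliably produce for delayed reactions.

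**Working it through.** **Inputs.** Session spacing of 6 weeks ± 1 week, that is 35 to 49 days (IV.D); call at 2 days and follow-up at 4 and 12 weeks, that is 28 and 84 days, after the last session (V.a); 15 subjects (IV.A).

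**The plan's own windows, reproduced from Day 1.** Session 2: 1 + 35 to 1 + 49 = Day 36 to 50. Session 3: 1 + 70 to 1 + 98 = Day 71 to 99. Session 4: 1 + 105 to 1 + 147 = Day 106 to 148. Calls at + 2: Day 38 to 52, 73 to 101, 108 to 150. Week 4: 106 + 28 to 148 + 28 = Day 134 to 176. Week 12: 106 + 84 to 148 + 84 = Day 190 to 232. All agree with V.a.

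**Days without scheduled contact.**

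| Interval | Calculation | Days |
|---|---|---|
| Call to next session (after sessions 1 to 3) | 35 − 2 to 49 − 2 | 33 to 47 |
| Call to Week 4 visit (after last session) | 28 − 2 | 26 |
| Week 4 to Week 12 visit | 84 − 28 | 56 |

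The longest gap is the last one.

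**The 30-day figure, as an analogy only.** Section I.B reports that "nodules were sometimes noted, resolving within 30 days at most", but in a phosphatidylcholine study. If a reaction of that length occurred here, it would clear before the next session if it began by post-injection day 35 − 30 = 5 (5-week spacing) or 49 − 30 = 19 (7-week spacing). After the last session it could not clear before the Week 4 visit, since 28 < 30.

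**Effect on the any-AE rate.** Let e be the proportion already positive from early reactions, d the proportion with a delayed transient AE, independent of e, and s the chance that a delayed AE is recalled. None of these is in the documents; all are assumptions.

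Loss = (1 − e) × d × (1 − s).

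- e = 0.60, d = 0.20, s = 0.5: 0.40 × 0.20 × 0.5 = 0.040, or 4 points (68% true, 64% recorded).
- e = 0.95, d = 0.10, s = 0.5: 0.05 × 0.10 × 0.5 = 0.0025, or about 0.3 points.

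**Effect on a delayed reaction considered alone.** The chance that at least one case is recorded among 15 subjects is 1 − (1 − d × s)^15.

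| d (assumed) | Full recall | 50% recall (assumed) |
|---|---|---|
| 5% | 54% | 32% |
| 10% | 79% | 54% |
| 20% | 96% | 79% |

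One subject missed or gained is 1/15 = 6.7 percentage points of the incidence of that reaction.

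**V.a against X.B.** X.B promises safety data at each visit. In V.a the first treatment visit has no AE item, and at later treatment visits the only AE item precedes the injection. An event in the clinic just after injection has no entry on that day's list and waits for the 2-day call.

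**The case against.** The strongest reply is that the primary endpoint is counted per patient. A subject who reports swelling or pain at the 2-day call is already positive, and nothing later changes that. A reader might infer that the whole primary endpoint rests on recall over 5 to 7 weeks. The documents do not support this: the any-AE rate would move by a few points at most under the assumptions above, and the visit after the last session is at 4 weeks. Nor are duration and severity listed endpoints.

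A reader might also take the 30-day nodules, and the bruising, edema and erythema of 48 to 72 hours, as figures for the study drug. Both come from the phosphatidylcholine study. For deoxycholic acid the only duration given in days is a median of 1 day for moderate-to-severe pain, which falls before the call. The gap itself does not depend on either figure.

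The supplied text is also incomplete. Section XI says the investigator reviews AEs as soon as they occur, which presupposes reports between visits. The post-treatment instructions, the consent form and the Schedule of Events are referred to but not reproduced, and may tell subjects when to call. So the claim is limited to scheduled contacts and to what the text describes. An event that has cleared can still be reported at the next visit, and the examination there may find residual signs. The call asks for events since the last treatment, so it does cover the hours after injection.

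All of this stands and narrows the point. It does not supply dates or severity for a reaction that begins after the call.

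**Conclusion.** The point holds for delayed transient reactions and is a low-cost improvement, not a defect that undermines the primary endpoint. The scheduled gaps are 33 to 47, 26 and 56 days, with no diary or symptom list described. The any-AE rate would lose about 0.3 to 4 points under assumed early rates of 60% to 95%, delayed rates of 10% to 20% and 50% recall. The larger loss is in the incidence by type, onset, duration and severity of delayed events, such as the ulcers and necrosis named in VII.A. If 5% to 10% of subjects had such an event and half were recalled, the chance of recording even one would fall from 54% to 79% down to 32% to 54%.

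A reader might go on to say that AE incidence is understated by 10% to 50%. That figure only restates an assumed recall of 90% to 50%, and it would apply to delayed events alone; the documents give no recall rate.

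The 26-day figure assumes that the last session is known to be the last by week 4. The plan does not say when that is decided for a subject who stops before session 4.

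**What to change.** 1. Give each subject a one-page diary at every session and again at Week 4, so that the 56-day gap is covered. List the reactions exactly as VII.A names them, each with start date, stop date and worst severity, and leave space for anything else. Collect it at the next visit and use it as an AE source alongside open questioning.
2. Read the same list at the existing 2-day calls.
3. Add an AE entry after the injection step at each treatment visit, including the first, so that V.a agrees with X.B.
4. State in VI.B that solicited and unsolicited AEs will be reported separately.

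Optionally, add one short call about 2 weeks after each session. It would split the 33 to 47 days into 12 (14 − 2) and 21 to 35 (35 − 14 to 49 − 14).

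Cost: one new form, used at most 5 times per subject (4 sessions plus Week 4), or 75 copies in all. The optional call adds at most 4 × 15 = 60 calls; at the 5 to 10 minutes the plan allows per call, that is 5 to 10 hours in total. The downside is that solicited reporting will raise recorded AE rates, hence item 4. Nothing here alters treatment.
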